4 HYPOTHESIS AND ROLE OF DISCUSSION

The statistical significance value is set at $p < 0.05$. The SPSS statistical package version 19.0 or later will be used.

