5 ANALYSIS SYSTEMS / POPULATIONS

Considering that 37% of COPD patients will have one moderate/severe exacerbation per year, and assuming that at least 35% of patients will follow their doctor's vaccination

recommendation,³ to have at least 200 vaccinated COPD patients with moderate/severe exacerbations, a total of 1541 eligible subjects should be included in the analysis.

With 35% of patients vaccinated with PCV13, enrolling 1541 eligible subjects with COPD would provide approximately 540 patients in the PCV13 cohort and 1000 patients in the unexposed cohort.

Assuming that 37% of unexposed patients will present one moderate/severe exacerbation per year,² with 70% of the patients remaining in the study after 1 year, this sample size would provide 91% power to detect a statistically significant reduction of 10% in moderate/severe COPD exacerbations with PCV13 after 1 year. Assuming an additional 30% dropout in the second year, the study sample size would provide 91% power to detect a statistically significant reduction of 14% in moderate/severe COPD exacerbations with PCV13 after 2 years.

Time	PCV13		Unexposed		Power	Retention rate
	Sample size	% exacerbation	Sample size	% exacerbation		
Enrollment	540		1000			
1 year	378	27%	700	37%	91.43%	70% from enrollment
2 years	264	60%	490	74%	91%	70% from year 1

5.1 **FULL ANALYSIS**

The statistical analysis of this study will be carried out with all those evaluable patients with COPD, recruited by the Spanish sites participating in the study and who meet the following selection criteria:

5.1.1 **Inclusion Criteria**

Patients must meet all of the following inclusion criteria to be eligible for inclusion in the study:

1. *Aged 18 years or older at the time consent is given*
2. *Patient diagnosed with COPD (any stage, subgroups for analysis will be based on COPD severity)*
3. *Evidence of a personally signed and dated informed consent document indicating that the patient has been informed of all pertinent aspects of the study.*
4. *Ability to understand and complete the required quality of life questionnaires*
5. *Patients with at least 2 years of previous clinical history available relating to (if applicable) history of moderate/severe exacerbations, influenza and pneumococcal vaccination history, comorbidities and previous treatments*
6. *Spirometry data* (maximum 6 months old, or if not available at enrollment, to be performed as per normal clinical practice at visit 1 ± one month)*

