The Student's t test, one-way ANOVA or its non-parametric equivalents, the Mann-Mann U test or Kruskal-Wallis H test will be used to determine if statistically significant differences are observed in NEPA, NEPA Mild, NEPA Moderate, NEPA Severe and NEPA Moderate/Severe according to the severity of COPD and type of patient (exposed/unexposed). In order to determine the impact of PCV13 vaccination on exacerbations, paired data comparisons will be made between (NEPA_pre_PCV13 vs. NEPA_post_PCV13) and (NEPA_pre_PCV13 (moderate/severe) vs. NEPA_post_PCV13 (moderate/severe)), using the Student's t-test for paired data or its non-parametric equivalent, the Wilcoxon test.

In order to study which subgroups of patients obtain a greater benefit from vaccination

with PCV13 according to COPD severity, paired data comparisons will be made between (NEPA_pre_PCV13 vs. NEPA_post_PCV13) and (NEPA_pre_PCV13 (moderate/severe) vs. NEPA_post_PCV13 (moderate/severe)), in each of the four patient subpopulations established based on disease severity.

In order to determine the factors associated with the presence of an exacerbator patient, a logistic regression model will be constructed, whose dependent variable is (exacerbator/non-exacerbator patient) and, as independent variables, all those possible factors that have been significant in the univariate models ($p_{value} < 0.25$), following the methodology of Hosmer-Lemeshow.

- ❖ Vaccine exposure (PCV13 yes/no)
- ❖ COPD severity (Grade I, Grade II, Grade III, Grade IV)
- ❖ Age
- ❖ Sex
- ❖ Time since diagnosis of the disease
- ❖ Patient with stable treatment for at least three months
- ❖

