8.2.3.4 COPD treatment

A detailed descriptive analysis of the treatments used by COPD patients will be performed. The absolute and relative frequency of patients who have received any of the following at some point during the disease will be given:

- Short-acting bronchodilators
 - Anticholinergics (SAMA) (ipratropium bromide, umeclidinium)
 - Short-acting β -2 agonists (SABA) (salbutamol, terbutaline)
- Long-acting bronchodilators
 - β -2 adrenergics (LABA) (salmeterol, formoterol indacaterol, vilanterol, olodaterol)
 - Anticholinergics (LAMA) (tiotropium bromide, aclidinium, glycopyrronium, umeclidinium)

- LABA+ LAMA
- Theophyllines
 - Theophylline +LABA+LAMA
 - Purified α -1-antitrypsin (AAT) replacement therapy
- Inhaled corticosteroids (IC): budesonide, fluticasone propionate, fluticasone furoate, beclomethasone, ciclesonide
 - IC+LABA
 - IC+LAMA
 - IC+LABA+LAMA
 - IC+ Theophylline
- Phosphodiesterase 4 (PDE4) inhibitors (Roflumilast)
 - PDE4 inhibitor+LABA
 - PDE4 inhibitor+LAMA
 - PDE4 inhibitor+LABA+LAMA
 - N-acetylcysteine (NAC)
- Antibiotics
 - Macrolides
 - Quinolones
- Other _____ specify

Additionally, the compliance of the patient will be described for each of the study progress visits through frequency distribution:

- ▣ Complies with treatment
- ▣ Does not comply with treatment
- ▣ Probably complies with treatment.

Using the Pearson's Chi-squared test or the Fisher's exact test for 2x2 tables or likelihood ratio for mXn tables, the study will examine whether there are statistically significant differences in the use of each of the treatments and the compliance of the patient according to the different analysis groups.

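### SAP 8.2.3.4 lists umeclidinium as both a short-acting and a long-acting anticholinergic, so the SAMA and LAMA rows are not uniquely defined

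*SAP*

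**What the plan says.** SAP 8.2.3.4 (COPD treatment) opens by describing its purpose: "A detailed descriptive analysis of the treatments used by COPD patients will be performed". It then says what will be tabulated: "The absolute and relative frequency of patients who have received any of the following at some point during the disease will be given". A list of classes follows, most with example drugs in brackets.

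- Under short-acting bronchodilators: "Anticholinergics (SAMA) (ipratropium bromide, umeclidinium".
- Under long-acting bronchodilators: "Anticholinergics (LAMA) (tiotropium bromide, aclidinium, glycopyrronium, umeclidinium".

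Six further rows combine LAMA with other classes: LABA+LAMA; theophylline+LABA+LAMA; inhaled corticosteroid+LAMA; inhaled corticosteroid+LABA+LAMA; PDE4 inhibitor+LAMA; and PDE4 inhibitor+LABA+LAMA.

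The section ends with chi-squared, Fisher or likelihood ratio tests of "statistically significant differences in the use of each of the treatments and the compliance of the patient according to the different analysis groups". SAP 5.4 and 8.2.1 give those groups as exposed/unexposed and COPD severity. SAP 6.1 lists pharmacological treatment among the secondary endpoints.

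**The concern.** The two headings are opposites: one is for short-acting agents, the other for long-acting agents. A patient who took two drugs may properly appear in two rows of an ever-use table. Here a patient who took one drug can appear in two opposing rows, or in either of them, depending on who programs the table. Two programmers could each follow the SAP and produce different SAMA and LAMA frequencies.

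What is at stake is limited but real. The study is not randomised, and these tables are one place where a reader will look for differences in COPD treatment between vaccinated and unvaccinated patients. The rows are also tested, so an error in a row's definition carries into a p-value.

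**Working it through.** **Text check.** The documents state no count, rate or power figure that depends on this point, so there is none to reproduce. The check is to apply the two lists to a patient whose only anticholinergic is umeclidinium.

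| Assignment | SAMA row | LAMA row and combinations with LAMA | Agreement with the SAP |
|---|---|---|---|
| Both classes (literal reading) | counted | counted | follows both lists; one row is overstated, because one drug cannot belong under both headings |
| SAMA only | counted | not counted | the LAMA list is not followed |
| LAMA only | not counted | counted | the SAMA list is not followed |

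No assignment both respects the opposed headings and follows both lists. SAP 8.2.3.4 contains no tie-breaking rule.

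**Illustration of size.** The inputs are:

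- Cohort sizes from SAP 5: "approximately 540 patients in the PCV13 cohort and 1000 patients in the unexposed cohort".
- Significance level 0.05 from SAP 4, taken as two-sided (assumption).
- Usage shares: assumed, since the documents give none.

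Call the row that should not contain umeclidinium the surplus row, without saying which it is. Let s be the share of patients who have used that row's other drugs, and u the share who have used umeclidinium. If the two are independent and every umeclidinium user is counted in the surplus row, that row reads

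r = s + u − s·u.

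*Equal use in both cohorts.* With s = 10% and u = 10%, r = 0.10 + 0.10 − 0.01 = 19% in each cohort. The level nearly doubles, but the difference between cohorts stays 0.

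*Unequal use.* Hold s equal in the two cohorts, so that any difference in the row comes only from umeclidinium. The chance that the test rejects is Φ((d − 1.96·SE0)/SE1), where d is the difference in r, SE0 the pooled standard error and SE1 the unpooled one, with 540 and 1000 patients.

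| s (both cohorts) | u exposed v unexposed | r exposed v unexposed | d | Chance of p < 0.05 |
|---|---|---|---|---|
| 10% | 15% v 10% | 23.5% v 19.0% | 4.5 points | about 55% |
| 10% | 20% v 10% | 28.0% v 19.0% | 9.0 points | about 98% |
| 30% | 15% v 10% | 40.5% v 37.0% | 3.5 points | about 27% |
| 30% | 20% v 10% | 44.0% v 37.0% | 7.0 points | about 76% |

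For the first line, the pooled share is (540 × 0.235 + 1000 × 0.190)/1540 = 0.2058, SE0 = 0.0216 and SE1 = 0.0221. This gives (0.045 − 1.96 × 0.0216)/0.0221 ≈ 0.12, and Φ(0.12) ≈ 0.55.

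**Reach.** The NEPA indices in SAP 8.2.3.1 count exacerbations over time and do not use drug class. The only treatment item visible among the factors of the exacerbator model there is "Patient with stable treatment for at least three months"; bronchodilator class is not listed, though the list ends in an empty bullet. SAP 8.2.3.6 plans treatment cost without a breakdown by class.

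**The case against.** The strongest reply is that this is a one-word slip in a descriptive list. The drugs in brackets may only be examples. Actual classification may be fixed by the case report form or the Data Management Plan, neither of which is shown; if sites record a class directly, nobody is counted twice. The rows already overlap by design, and no primary result depends on them.

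Much of that stands, and it rules out several stronger readings that a reader might infer.

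- *Every umeclidinium user will be counted twice.* This is the literal reading of the lists, not a stated rule, and the coding is not shown.
- *A comparison of short-acting with long-acting treatment between cohorts is invalid.* No such comparison is planned. Each treatment is tested separately across the groups.
- *The tests between groups are wrong.* Under double counting, a difference arises only if umeclidinium use also differs between the groups. With equal use the level is wrong and the difference is not.
- *SAMA is the inflated row.* The documents show only that the lists conflict, not which entry is the error.
- *Adjustment for confounding is compromised.* Bronchodilator class is not among the potential confounders named in SAP 8.1 or the visible model factors in 8.2.3.1.

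The reply does not remove the contradiction. An analysis plan should not leave a printed class definition to be settled by documents it does not cite, and overlap between rows for patients on several drugs does not explain one drug under two opposed headings.

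**Conclusion.** The SAP is wrong as written, and the point is minor. The SAMA and LAMA definitions in 8.2.3.4 cannot both hold. Followed literally, at least one of the two frequencies is wrong as soon as one umeclidinium user has taken no other drug in the surplus row. If umeclidinium users are placed in one class, one printed definition is ignored, and the six combination rows that contain LAMA depend on the choice.

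The real size cannot be stated, because the documents give no usage figures. The percentages and rejection rates above rest on assumed shares, independent use, double counting and the planned cohort sizes; they show what could happen, not what will. The NEPA comparisons and the visible factors of the logistic model are not affected.

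**What to change.** The sponsor's medical reviewer should reconcile the two umeclidinium entries so that the drug stands in one class. The SAP, or a coding table that it cites, should then map each listed drug to a single class, and the SAMA, LAMA and combination rows should all be derived from that table. A patient who took drugs from several classes would still appear in several rows, as the ever-use design intends. The class recorded in the case report form should be checked against the same table before the treatment tables are run.

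The cost is one word in the SAP and one line in the coding table. No new data or change in sample size is needed.

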8.2.3.5 Vaccination history

The absolute and relative frequencies of patients who have a vaccination history of the following will be given:

- Pneumococcal vaccination
- Influenza vaccination

In the subpopulation of patients with pneumococcal vaccination, the frequency

distribution will be presented according to the type of pneumococcal vaccine:

- ✓ Polysaccharide
 - 1 dose
 - 2 doses
 - 3 doses
 - 4 doses
 - No. of doses unknown
- ✓ Conjugate
 - History of influenza vaccination, in the same year in which the conjugate vaccine is received

The study will look at whether there are statistically significant differences in the patient's vaccination history according to the severity of COPD, using the significance level test.

8.2.3.6 Disease-related costs

The mean, standard deviation, median, minimum, maximum, IR and CI 95% of the costs derived from the following will be shown:

- Hospital admission and cost of exacerbations
- Treatment

The Student's t test, one-way ANOVA or its non-parametric equivalents, the Mann-Mann U test or Kruskal-Wallis H test, will be used to determine if statistically significant differences are observed in the disease-related costs according to the severity of COPD and type of patient (exposed/unexposed).

For the subpopulation of vaccinated patients, the related costs per patient and year will be calculated in the pre-vaccination/post-vaccination period.

In order to determine the impact of vaccination with PCV13 on the disease-related costs, paired data comparisons will be made between (related cost patient year_pre_PCV13 vs. related cost patient year_post_PCV13), using the paired Student t-test or its non-parametric equivalent, the Wilcoxon test.

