## 7. RESEARCH QUESTION AND OBJECTIVES

- **Primary objectives**

1. Evaluate the impact of routine clinical practice vaccination with PCV13 on the reduction of the risk of COPD moderate/severe exacerbations (see definitions) in adults, after 2 years of follow up.
2. Determine which subgroup of patients (based on the severity of COPD) benefit most from vaccination with PCV13  
COPD severity (GOLD)
  - GRADE 1: Mild/unknown [FEV1≤ 80%, FEV1/FVC < 0,7 or no spirometry data]
  - GRADE 2: Moderate [50% ≤ FEV1< 80%, FEV1/FVC < 0,7]
  - GRADE 3: Severe [30% ≤ FEV1 < 50%, FEV1/FVC < 0,7]
  - GRADE 4: Very severe [FEV1< 30% o FEV1< 50% plus respiratory failure, FEV1/FVC < 0,7])

- **Secondary objectives**

1. Evaluate the impact of influenza and PCV13 vaccination on the reduction of the risk of exacerbations
2. Evaluate the impact of vaccination with PCV13 on patients' quality of life
3. Evaluate the impact of vaccination with PCV13 on the decrease of FEV1
4. Estimate the potential economic savings for the healthcare system derived from vaccination of COPD patients with PCV13
5. Determine the prevalence of PCV13 vaccination in COPD patients.

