The aim of this study is to generate evidence to support vaccination of COPD patients with PCV13 and/or against influenza in terms of clinical benefits and quality of life.

2.1 **STUDY DESIGN**

Prospective observational study, which will be carried out in 6 different geographical areas in Spain (Salamanca, Cantabria, Palma de Mallorca, Madrid, Barcelona and Seville), involving 1 hospital in each region.

Subjects identified with COPD will be invited to participate by investigators at the time of their routine follow-up visits. All therapies will be prescribed in line with routine clinical practice according to the updated National COPD Guidelines (GesEPOC),¹ indicating among other therapies active reduction of risk factors, and influenza and pneumococcal vaccination (with PCV13) in all patients with mild, moderate or severe COPD. All patients will be advised to quit smoking and recommended healthy lifestyle habits.

Study will include periodic visits for all patients, to complete a total follow up of 2 years.

2.2 **STUDY OBJECTIVES**

The study objectives are to:

- **Primary objectives**

1. Evaluate the impact of routine clinical practice vaccination with PCV13 on the reduction of the risk of moderate/severe COPD exacerbations, after 2 years of follow-up.
2. Determine which subgroup of patients (based on the severity of COPD) benefit most from vaccination with PCV13

COPD severity (GOLD)¹⁸

- GRADE 1: Mild/unknown [$FEV1 \geq 80\%$, $FEV1/FVC < 0.7$ or no spirometry record]
- GRADE 2: Moderate [$50\% \leq FEV1 < 80\%$, $FEV1/FVC < 0.7$]
- GRADE 3: Severe [$30\% \leq FEV1 < 50\%$, $FEV1/FVC < 0.7$]
- GRADE 4: Very severe [$FEV1 < 30\%$ or $FEV1 < 50\%$ plus respiratory failure, $FEV1/FVC < 0.7$])

- **Secondary objectives**

1. Evaluate the impact of influenza and PCV13 vaccination on the reduction of the risk of exacerbations
2. Evaluate the impact of vaccination with PCV13 on patients' quality of life
3. Evaluate the impact of vaccination with PCV13 on the decrease in FEV1
4. Estimate the potential savings for the healthcare system derived from vaccination of COPD patients with PCV13
5. Determine the prevalence of PCV13 vaccination in COPD patients.

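### The savings objective rests on a disease-related cost comparison that names no PCV13 vaccination cost, so any saving read from it is gross, not net

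*SAP*

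**What the plan says.** Both documents set the same secondary economic objective. Protocol section 7 words it as "Estimate the potential economic savings for the healthcare system derived from vaccination of COPD patients with PCV13"; SAP section 2.2 has "Estimate the potential savings for the healthcare system derived from vaccination of COPD patients with PCV13".

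The one SAP section that analyses cost is 8.2.3.6, Disease-related costs. It lists two components, "Hospital admission and cost of exacerbations" and *Treatment*, and does not define the second. Costs are to be compared by COPD severity and between exposed and unexposed patients. For vaccinated patients, "the related costs per patient and year will be calculated in the pre-vaccination/post-vaccination period". The purpose given is: "In order to determine the impact of vaccination with PCV13 on the disease-related costs, paired data comparisons will be made", the contrast being "related cost patient year_pre_PCV13 vs. related cost patient year_post_PCV13".

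Two neighbouring sections bear on what *Treatment* can mean:

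- SAP 8.2.3.4, COPD treatment: "A detailed descriptive analysis of the treatments used by COPD patients will be performed". Its list covers bronchodilators, theophyllines, antitrypsin replacement, inhaled corticosteroids, PDE4 inhibitors, N-acetylcysteine, antibiotics and an open entry for others. No vaccine is named.
- SAP 8.2.3.5, Vaccination history: "The absolute and relative frequencies of patients who have a vaccination history of the following will be given". No cost is attached.

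No price, price year or costing source appears in the protocol or SAP text. The protocol lists an Annex 6 with the title Economic report; its content is not in the text available.

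**The concern.** The health system pays for vaccination. A saving attributed to vaccination should therefore be what is left after that payment. If the difference in disease-related cost is reported as the answer to the savings objective, the cost of the intervention is missing from the side of the comparison that received it. The resulting error has a known direction and does not shrink with more patients or longer recruitment. Depending on the price of vaccination relative to the cost of an exacerbation, it could change the conclusion from a net saving to a net cost. No other analysis in the SAP would reveal this, because no other analysis addresses the objective.

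**Working it through.** The documents state no cost or savings figure, so there is nothing of the plan's own to reproduce. The check has two parts: what the plan would count, and what leaving V out does to the result.

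**1. Would *Treatment* pick up the vaccine?** The documents keep the two apart in every place where both are listed as data:

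- Protocol 8.3 and SAP 6.1 have separate entries for drug treatment and for pneumococcal vaccination.
- Protocol Table 1 has one row for the PCV13 record and another for the updated treatment record.
- SAP 8.2.3.4 and 8.2.3.5 are separate sections, and only the first lists treatments.

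An analyst costing *Treatment* from these data would use the drug list and leave the vaccine out.

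**2. Effect on the result.** Notation, per vaccinated patient:

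- V = acquisition plus administration cost of PCV13 (not in the documents)
- C = cost per patient with a moderate or severe exacerbation over the period (not in the documents; taken as equal in both groups)
- ARR = absolute reduction in the proportion with an exacerbation
- T = post-vaccination years

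Differences in other treatment cost are set to zero for this illustration.

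Cumulative cost: gross saving = ARR × C; net saving = ARR × C − V. The gross figure exceeds the net by V.

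Per patient-year: gross = ARR × C / T; net = (ARR × C − V) / T. The gross figure exceeds the net by V/T, which is V/2 at T = 2.

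On either scale, break-even is V/C = ARR, and V takes up the share V / (ARR × C) of the gross saving.

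Inputs for ARR:

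- Protocol 8.5, 1 year: 0.37 − 0.27 = 0.10, so 1/0.10 = 10 vaccinated per patient spared.
- Protocol 8.5, 2 years: 0.74 − 0.60 = 0.14, so 1/0.14 = about 7.1 vaccinated per patient spared.
- Illustration only: Protocol 8.9 cites a 5% non-significant reduction in all-cause pneumonia from a large trial. If a 5% relative reduction applied to the 74% two-year risk, ARR = 0.05 × 0.74 = 0.037, so 1/0.037 = about 27 vaccinated per patient spared.

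V as a share of the gross saving, for assumed V/C:

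| V/C (assumed) | ARR 0.10 (1 year) | ARR 0.14 (2 years) | ARR 0.037 (illustration) |
|---|---|---|---|
| 0.02 | 20% | 14% | 54% |
| 0.05 | 50% | 36% | 135% |
| 0.10 | 100% | 71% | 270% |
| 0.20 | 200% | 143% | 541% |

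Above 100% the net result is a cost, although the gross figure still shows a saving.

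**3. Units matter for the remedy.** Adding the whole of V to a per-year cost would overcorrect. At T = 2 and ARR 0.14, the yearly gross saving is 0.14 × C / 2 = 0.07 × C, so an undivided V would move the apparent break-even from V/C = 0.14 to 0.07. V and the other costs must share one time scale.

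**The case against.** The strongest reply is that 8.2.3.6 does what its title says. It compares disease-related cost, and a vaccine price does not belong in that quantity. The objective speaks of potential savings, and no formula turns the cost difference into a savings figure. This stands: the comparison is valid on its own terms, and a reader who infers that the planned analysis is wrong goes beyond the text. What remains is that nothing else in the SAP answers the objective, so this difference is what would be offered as the saving.

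Second, *Treatment* is undefined, the list in 8.2.3.4 has an open entry, and Protocol 8.2 and SAP 2.1 mention vaccination among guideline therapies. Annex 6 may also contain costing rules. So it cannot be said that the vaccine is excluded beyond doubt. But none of this puts its cost into the plan, and the separate recording of treatment and vaccination points the other way.

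Third, a reader might infer that the reported figure will always favour the vaccine. The documents do not support that. Leaving V out shifts the estimate in one direction but does not fix its sign. Protocol section 6 says exacerbations become more frequent as COPD progresses, so cost after vaccination may exceed cost before it, and the exposed/unexposed contrast is not randomised.

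Fourth, a reader might want a euro total from an assumed price times the 540 vaccinated patients expected at enrolment. No price is given, the plan expects 378 and 264 of them to remain at 1 and 2 years, and no planned output is such a total. That figure should not be used.

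**Conclusion.** The point holds in a limited form. The SAP's cost comparison is sound as a description of disease-related cost. Used to answer the savings objective, it gives a gross figure, shifted in the vaccine's favour by V per vaccinated patient on cumulative cost, or by V/T on the per-patient-year scale planned for the pre/post contrast.

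The amount is unknown because the documents give neither V nor C. At the protocol's design effects, vaccination saves money only if V is below 10% (1 year) or 14% (2 years) of the cost per patient with exacerbation; at the illustrative 5% relative effect the threshold is 3.7%. These thresholds assume equal C in the two groups and no difference in other treatment cost. They show that a change of sign is possible, not that it will occur.

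This is a secondary objective, and the gap is best closed before results are reported.

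**What to change.** In SAP 8.2.3.6:

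- Define *Treatment* and say whether any vaccine cost is in it.
- Keep the planned comparison and label it gross.
- Add a net result that includes PCV13 acquisition and administration for each exposed patient, on the same time scale as the other costs: either cumulative cost over follow-up with V counted once, or the per-year index with V spread over post-vaccination person-time.
- State the unit-cost source and price year.
- Treat PPV23 and influenza vaccine by the same rule in both groups.
- Vary V in a sensitivity analysis and report the break-even value.
- Add a cost table to the exposed/unexposed set. SAP section 9 lists disease-related costs only under the severity tables, although 8.2.3.6 plans both comparisons.

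Receipt of PCV13 and influenza vaccine is already recorded at study visits, and pneumococcal vaccination history, including polysaccharide doses, is already summarised, so no new patient data should be needed. The cost is one more cost item with a documented source, some programming, and a reported saving less favourable than the gross one.
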